### **Herpes Simplex**

A summary analysis of herpes simplex will be provided. Herpes simplex will be defined based on MedDRA PT as listed in Compound level safety standards (both narrow and broad terms in the herpes simplex section). The list is reviewed by GPS/medical prior to data locks (final and interim). The summary table will include event maximum severity, seriousness, whether resulting in temporary study drug interruption, whether resulting in study drug discontinuation, and whether treated with antiviral medication.

If a patient has more than 1 event of herpes simplex, the event with the maximum severity will be used in these summary tables. If more than 1 event of herpes simplex occurs with the same severity, the event with the longest duration will be used in the summary table.

### **Skin Infections**

A summary analysis of skin infections may be provided. Skin infections may be defined based on MedDRA preferred term as listed in Compound level safety standards.

### **HBV DNA**

A listing of patients with detectable HBV DNA postbaseline will be provided.

HBV DNA status post baseline (not detectable, detectable but not quantifiable [that is, < lower limit of detection (LLOD)], quantifiable [that is,  $\geq$ LLOD]) will be summarized by treatment group stratified by baseline HBV serology status, specifically:

1. HBsAb+ / HBcAb+
2. HBsAb- / HBcAb+

### **Association Between Infection and Neutropenia/Lymphopenia**

Depending on the number of cases with CTCAE Grade 2 or greater, a summary table may be provided for treatment-emergent infections that were preceded or accompanied by neutropenia. For this analysis, neutropenia is defined as (1) CTCAE Grade 2 or greater or (2) CTCAE Grade 3

or greater. Infection events with onset date  $\leq$ 14 days before or after the Grade 2 or greater neutrophil count collection date will be considered as infections preceded or accompanied by neutropenia.

Similar analyses as above will be conducted to evaluate the association between infection and lymphopenia.

#### **6.13.4.7. Major Adverse Cardiovascular Events and Other Cardiovascular Events**

Potential major adverse cardiovascular events (MACE) and other cardiovascular events requiring adjudication will be analyzed.

Categories and subcategories analyzed will include, but are not limited to the following:

- MACE
  - Cardiovascular death
  - Myocardial infarction (MI)
  - Stroke
- Other cardiovascular events
  - Transient ischemic attack
  - Hospitalization for unstable angina
  - Hospitalization for heart failure
  - Serious arrhythmia
  - Resuscitated sudden death
  - Cardiogenic shock
  - Coronary interventions (such as coronary artery bypass surgery or percutaneous coronary intervention)
- Non-cardiovascular death
- All-cause death

In general, events requiring adjudication are documented by investigative sites using an endpoint reporting CRF. This CRF is then sent to the adjudication center which uses an adjudication reporting CRF to document the final assessment of the event as a MACE, as some other cardiovascular event, or as no event (according to the Clinical Endpoint Committee Charter). In some cases, however, the investigator may not have deemed that an event had met the endpoint criteria, but the event was still sent for adjudication as a potential MACE, other cardiovascular event, or no event. These events are included in the adjudication process to ensure adequate sensitivity. In these instances, the adjudication reporting CRF will not have a matching endpoint reporting CRF from the investigator. Events generated from these circumstances will be considered as events sent for adjudication in the absence of an investigator's endpoint reporting form.

The number and percentage of patients with MACE, other cardiovascular events, non-cardiovascular death, and all-cause death, as positively adjudicated, will be summarized by treatment group based on the categories and subcategories above.

A listing of the events sent for adjudication will be provided to include data concerning the MedDRA PT related to the event, the seriousness of the event, and the event outcome, along with the adjudicated result.

#### **6.13.4.8. Venous Thromboembolic (VTE) Events**

Events identified as representative of venous thromboembolic event (VTE) disease will be further classified as deep vein thrombosis (DVT), pulmonary embolism (PE), or other peripheral venous thrombosis and will be analyzed. The following definitions apply:

- DVT: Clinical diagnosis of a thrombosis in a deep vein above the knee that must be confirmed by objective evidence of either: a filling defect of deep veins of the leg on venography or a non-compressible venous segment on ultrasound or confirmation by other imaging modality (for example, computed tomography [CT], magnetic resonance imaging [MRI])
- PE: Clinical diagnosis of pulmonary embolus that must be confirmed by objective evidence of either: a filling defect of pulmonary arteries by either pulmonary angiography or CT angiography or by a high probability ventilation perfusion (VQ) scan
- Other Peripheral Venous Thrombosis: Clinical diagnosis of a venous thrombosis not specified by either DVT or PE above. Other peripheral venous thrombosis must be confirmed by objective evidence by imaging including venography, ultrasound, CT scan, or MRI. Examples of these would include non-superficial below knee thrombosis, portal vein thrombosis, subclavian vein thrombus, or mesenteric vein thrombus. Superficial thrombophlebitis alone is not considered a VTE event.

In general, events requiring adjudication are documented by investigative sites using an endpoint reporting CRF. Refer to Section [6.13.4.7](#) for more details, as the process is the same as that for MACE.

The number and percentage of patients with a VTE, DVT/PE, DVT, PE, and other peripheral venous thrombosis, as positively adjudicated, will be summarized by treatment group.

A listing of the VTE events sent for adjudication will be provided to include data concerning the MedDRA PT related to the event, the seriousness of the event, and the event outcome, along with the adjudicated result.

#### **6.13.4.9. Arterial Thromboembolic Events**

Refer to the Compound level safety standards.

#### **6.13.4.10. Malignancies**

Malignancies will be identified using terms from the malignant tumors SMQ (SMQ 20000194). Malignancies excluding non-melanoma skin cancers (NMSC) and NMSC will be reported separately.

All the cases identified by malignant tumors SMQ will be assessed through medical review to determine confirmed NMSC cases.

First, a listing including all the malignancy cases will be prepared before DBL, along with the *planned* NMSC flag according to the current MedDRA version PTs:

- Squamous cell carcinoma of skin (10041834)
- Bowen's disease (10006059)
- Basal cell carcinoma (10004146)
- Basosquamous carcinoma (10004178)
- Basosquamous carcinoma of skin (10004179)
- Squamous cell carcinoma (10041823)
- Skin squamous cell carcinoma metastatic (10077314)
- Skin cancer (10040808)
- Carcinoma in situ of skin (10007390)
- Keratoacanthoma (10023347)
- Vulvar squamous cell hyperplasia (10079905)
- Skin squamous cell carcinoma recurrent (10081136)
- Basal cell carcinoma metastatic (10083708)

This internal review is to occur prior to DBL. The case review and subsequent summary analyses will include all the cases reported in the study database or by Lilly Safety System report, disregarding the length of gap between the last treatment dose date and the event date. The NMSC flag will be confirmed by the medical team during the internal review process.

The number and percentage of patients with TEAE malignancies excluding NMSC and NMSC will be summarized by treatment group.

#### **6.13.4.11. Allergic Reactions/Hypersensitivities**

A search will be performed using the current MedDRA version SMQs to search for relevant events, using the following queries:

- Anaphylactic reaction SMQ (20000021)
- Hypersensitivity SMQ (20000214)
- Angioedema SMQ (20000024)

Refer to the Compound safety level standards for details.

#### **6.13.4.12. Gastrointestinal Perforations**

Treatment-emergent adverse events related to potential gastrointestinal (GI) perforations will be analyzed using reported AEs. Identification of these events will be based on review of the PTs of the MedDRA SMQ 20000107, GI perforations (note that this SMQ holds only narrow terms and has no broad terms). Potential GI perforations identified by the above SMQ search will be provided as a listing for internal review by the medical safety team. Each case will be assessed to determine whether it is GI perforation. A summary table based on medical review may be provided and treatment comparisons will be made using Fisher's exact test.

#### **6.13.4.13. Columbia-Suicide Severity Rating Scale**

Suicidal ideation, suicidal behavior, and self-injurious behavior without suicidal intent, based on the C-SSRS, will be listed by patient and visit. Only patients that show suicidal

ideation/behavior or self-injurious behavior without suicidal intent during treatment will be displayed along with all their ideation and behavior, even if not positive (that is, if a patient's answers are all 'no' for the C-SSRS, then that patient will not be displayed). A summary of the C-SSRS categories during treatment and a shift summary in the C-SSRS categories from baseline during treatment may be provided.

#### **6.13.4.13.1. Self-Harm Supplement Form and Self-Harm Follow-up Form**

The Self-Harm Supplement Form is a single question to enter the number of suicidal behavior events, possible suicide behaviors, or nonsuicidal self-injurious behaviors. If the number of behavioral events is greater than zero, it will lead to the completion of the Self-Harm Follow-Up Form. The Self-Harm Follow-Up Form is a series of questions that provides a more detailed description of the behavior cases. A listing of the responses give on the Self-Harm Follow-Up Form will be provided.

### **6.14. Subgroup Analyses**

**In Period 2**, subgroup analyses comparing each dose of baricitinib to placebo will be performed on the ITT population **at Week 16**, with data up to rescue (primary censoring rule) for the following:

- Proportion of patients achieving IGA 0 or 1 with a 2-point improvement
- Proportion of patients achieving EASI75 Response Rate
- Proportion of patients achieving Itch NRS 4-point improvement

The following subgroups, categorized into disease-related characteristics and demographic characteristics, will be evaluated:

- Patient Demographic and Characteristics Subgroups:
  - Gender (male, female)
  - Age group (<65 years,  $\geq$ 65 years)
  - Age group (<65 years,  $\geq$ 65 years to <75 years,  $\geq$ 75 years to <85 years,  $\geq$ 85 years)
  - Baseline weight: (<60 kg,  $\geq$ 60 kg to <100 kg,  $\geq$ 100 kg)
  - Baseline BMI (<25 kg/m^2,  $\geq$ 25 kg/m^2 to <30 kg/m^2,  $\geq$ 30 kg/m^2)
  - Race: (American Indian or Alaska Native, Asian, Black or African American, Native Hawaiian or Other Pacific Islander, White, Multiple)
  - Ethnicity (Hispanic, non-Hispanic)
  - Baseline renal function status: impaired (eGFR <60 mL/min/1.73 m^2) or not impaired (eGFR  $\geq$ 60 mL/min/1.73 m^2)
- Geographic Region Subgroups:
  - Region (as defined in )
  - Specific regions (Europe, other)
  - Specific country (Japan, other)

- Previous and Concomitant Therapy Subgroups:
  - Prior use of TCNI (yes, no)
  - Prior systemic therapy use (yes, no)
- Baseline Disease-Related Characteristics Subgroup:
  - Baseline disease severity (IGA score: 3, 4)

Descriptive statistics will be provided for each treatment and stratum of a subgroup as outlined, regardless of sample size.

Subgroup analyses for categorical outcomes will be performed via logistic regression, using Firth's correction to accommodate (potential) sparse response rates. The model will include the categorical outcome as the dependent variable and baseline value (for EASI and itch), treatment, subgroup, and treatment-by-subgroup interaction as explanatory variables. Missing data will be imputed using NRI (Section 6.3.1). The treatment-by-subgroup interaction will be tested at the 0.1 significance level. The p-value from the logistic regression model will be reported for the interaction test and the subgroup test, unless the model did not converge. Response counts and percentages will be summarized by treatment for each subgroup category. The difference in percentages and 95% confidence interval (CI) of the difference in percentages using the Newcombe-Wilson without continuity correction will be reported. The corresponding p-value from the Fisher's exact test will also be produced.

In case any level of a subgroup comprises <10% of the overall sample size, only descriptive summary statistics will be provided for treatment arms, and no treatment group comparisons will be performed within these subgroup levels.

Additional subgroup analyses on efficacy may be performed as deemed appropriate and necessary.

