10.3.6.2. Subgroup Analyses

To assess whether the treatment effect is similar across subgroups for the primary efficacy outcome, a logistic model will be used and will include treatment, stratification variables (disease severity; region as appropriate), the subgroup variable (e.g., sex), and the subgroup-by-treatment interaction. If the interaction is statistically significant at $\alpha = 0.10$, the nature of the interaction will be explored, that is, within each subgroup the treatment effect will be estimated. Similarly, for the continuous variables of EASI, the MMRM model will include additional variables for subgroup and the subgroup by treatment interaction.

Treatment effects for subgroups defined by IGA, age, race, sex, and region (as appropriate) will be assessed and reported regardless of whether the interaction test is significant or not.

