**Figure JAIN.5.1.**

**Illustration of study design for Clinical Protocol I4V-MC-JAIN.**

## 5.1. Method of Assignment to Treatment

**At Week 0 (Visit 2),** patients who meet all criteria for enrollment will be randomized in a 1:1:2:1 ratio to receive double-blind treatment with placebo QD, baricitinib 1-mg QD, 2-mg QD, or 4-mg QD. Randomization will be stratified by geographic region and disease severity at baseline (IGA 3 vs 4). Assignment to treatment groups will be determined by a computer-generated random sequence using an interactive web-response system (IWRS). The IWRS will be used to assign cartons, each containing 4 blister packs of double-blind investigational product tablets to each patient, starting at Visit 2 (Week 0), and at each visit up to and including Visit 27 (Week 184). Site personnel will confirm that they have located the correct carton by entering a confirmation number found on the carton into the IWRS.

This study will be conducted internationally at multiple sites.

Table JAIN.5.1 below describes how regions will be defined for stratification. Regions may be combined for statistical analyses when one of the region strata fails to meet the minimum number of patients. Details are provided in Section 6.2.2.2.

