### 6.2.2.2. Covariate Adjustment

This study will be conducted by multiple investigators at multiple sites internationally, and countries will be categorized into geographic regions (see [Table JAIN.5.1](#)). Randomization to treatment groups at Week 0 (Visit 2) is stratified by disease severity (IGA) and geographic region as described in [Section 5.1](#). Unless otherwise specified, the statistical analysis models will adjust for disease severity and geographical region.

The covariates used in the logistic model for categorical data will include the parameter value at baseline. The covariates used in the analysis of covariance (ANCOVA) model for continuous data will include the parameter value at baseline. Inclusion of baseline in the model ensures that treatment least-squares means (LSMs) are estimated at the same baseline value. When a mixed-model repeated measures (MMRM) analysis is performed, baseline value and baseline-by-visit interactions will be included as covariates.

Unless otherwise specified, all analyses described in this section will compare estimates (for example, odds ratios, LSMs, proportions) of baricitinib 4-mg, 2-mg, and 1-mg to placebo. Thus, odds ratios are for baricitinib treatment groups relative to placebo; similarly, LSM differences and differences in proportions are between baricitinib treatment groups and placebo.

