### 6.2.2.3. Analysis Method

The main analysis of categorical efficacy variables and health outcomes variables will use a logistic regression analysis with region (as appropriate), baseline disease severity (IGA), baseline value, and treatment group in the model. Firth's correction will be used in to accommodate (potential) sparse response rates. The p-value for the odds ratio from the logistic regression model will be used for statistical inference, unless Firth's correction still results in quasi-separation. In that case, Fisher's exact test will be used for statistical inference. The difference in percentages and 100(1-alpha)% CI of the difference in percentages using the Newcombe-Wilson without continuity correction will be reported. The p-value from the Fisher's exact test will also be produced as a secondary analysis.

In case geographic region is used as factor in the statistical model, for the analysis of the primary endpoint, treatment-by-region interaction will be added to the logistic regression model as a sensitivity analysis and results from this model will be compared to the primary model (without the interaction effect). If the treatment-by-region interaction is significant at a 2-sided  $\alpha$  level of 0.1, the nature of this interaction will be inspected as to whether it is quantitative (that is, the treatment effect is consistent in direction across all regions but not in size of treatment effect) or qualitative (the treatment is beneficial in some but not all regions). If the treatment-by-region interaction effect is found to be quantitative, results from the primary model will be presented. If the treatment-by-region interaction effect is found to be qualitative, further inspection will be used to identify in which regions baricitinib is found to be more beneficial.

The main analysis method for all continuous efficacy and health outcomes variables will use MMRM analysis. The MMRM model will use a restricted maximum likelihood (REML) estimation. The model will include treatment, region (as appropriate), baseline disease severity (IGA), visit, and treatment-by-visit-interaction as fixed categorical effects and baseline and baseline-by-visit-interaction as fixed continuous effects.

For daily diary assessments and the model for 24-week interim analyses, the following models will be generated:

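### The subgroup logistic model in SAP 6.14 leaves out disease severity and region, which the protocol's subgroup model includes: restore them or justify the departure

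*SAP*

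**What the plan says.** Protocol 10.3.6.2 says the logistic model for subgroups of the primary outcome "will include treatment, stratification variables (disease severity; region as appropriate), the subgroup variable" and the subgroup-by-treatment interaction.

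SAP 6.14 covers three Week 16 endpoints: IGA (0,1), EASI75 and 4-point itch improvement. Its model takes the baseline value, for EASI and itch only, with "treatment, subgroup, and treatment-by-subgroup interaction as explanatory variables". It also states that "The treatment-by-subgroup interaction will be tested at the 0.1 significance level". From this model it reports p-values for the interaction and for the subgroup. Treatment effects within subgroups are given as differences in percentages with Newcombe-Wilson intervals and Fisher p-values.

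Elsewhere the SAP treats the two factors as standard. Section 5.1 stratifies randomisation by region and by IGA 3 versus 4. Section 6.2.2.3 defines the main categorical analysis as a "logistic regression analysis with region (as appropriate), baseline disease severity (IGA), baseline value, and treatment group in the model". Section 6.2.2.2 gives a default: "Unless otherwise specified, the statistical analysis models will adjust for disease severity and geographical region".

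**The concern.** SAP 6.14 writes out its own covariate list and gives no reason for leaving out the two stratification factors. The revision history for Versions 3 to 5 records no change to that section. Because 6.14 neither invokes nor waives the 6.2.2.2 default, one programmer could add severity and region while another leaves them out. They would then report different interaction p-values from what is meant to be one prespecified analysis.

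The gap is widest for IGA (0,1), where 6.14 keeps no baseline value. Patients enter at IGA 3 or 4, and response means reaching 0 or 1 with at least a 2-point gain. A patient starting at 4 must improve by at least 4 − 1 = 3 points; a patient starting at 3 needs 3 − 1 = 2. The endpoint definition itself therefore makes baseline IGA plausibly prognostic.

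Odds ratios are non-collapsible. Leaving a prognostic factor out of a logistic model generally pulls the interaction coefficient towards zero and costs power. At stake is how sensitive the interaction tests are, and whether they match the model the protocol promised.

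**Working it through.** **1. The models side by side**

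| Source | Endpoint | Severity | Region | Baseline value |
|---|---|---|---|---|
| Protocol 10.3.6.2 | EASI75 (primary outcome) | yes | as appropriate | not listed |
| SAP 6.14 | EASI75, itch | no | no | yes |
| SAP 6.14 | IGA (0,1) | no | no | no |
| SAP 6.2.2.3 main model | categorical efficacy | yes | as appropriate | yes |

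For EASI75 the SAP list departs from the protocol's subgroup model. For IGA (0,1) and itch, which the protocol's subgroup paragraph does not name, it departs from the SAP's own main model. Severity or region does enter the 6.14 model when it is the subgroup being tested.

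**2. The plan's own power figure**

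The documents give no power for any interaction. The primary figure (SAP 6.1) is more than 90% for 20% versus 45% at two-sided 0.025 (z = 2.241). Power = Φ{[0.25 − z·SE₀]/SE₁}, where SE₀ is pooled and SE₁ unpooled.

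- 100 v 100: SE₀ = √(2 × 0.325 × 0.675/100) = 0.0662; SE₁ = √((0.16 + 0.2475)/100) = 0.0638. Power = Φ(1.59) = 94.4%.
- 100 v 200: SE₀ = 0.0590; SE₁ = 0.0533. Power = Φ(2.21) = 98.6%.

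The stated figure is reproduced.

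**3. What omission does to the interaction test**

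From the documents: 20% and 45% response, arms of 100, 100 and 200, interaction level 0.10. Assumed, because the documents are silent: subgroup split 50/50, 50% at IGA 4, regions 65/20/15, a true interaction odds ratio (OR) of 2 to 4, and prognostic ORs varied as below (an OR under 1 means a lower chance of response).

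Logistic models with and without severity and region were fitted to the expected cell probabilities. Wald power = Φ(|b|/SE − 1.645) + Φ(−|b|/SE − 1.645).

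Worked case, severity OR 0.25, region OR 0.33, interaction OR 3, 100 v 100:

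- With strata: b = 1.099, SE = 0.693, ratio 1.586, power 47.7%.
- Without: b = 0.940, SE = 0.649, ratio 1.448, power 42.3%.
- Shrinkage 1 − 0.940/1.099 = 14.5%; loss 5.4 points.

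All settings at interaction OR 3:

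| Severity OR / region OR | Shrinkage | Power with v without strata, 100 v 100 | Loss, 100 v 100 | Loss, 100 v 200 |
|---|---|---|---|---|
| 1 / 1 | 0% | identical | 0 | 0 |
| 0.7 / 0.8 | 1.0% | 51.4% v 51.0% | 0.4 | 0.5 |
| 0.5 / 0.7 | 3.4% | 50.8% v 49.5% | 1.3 | 1.5 |
| 0.33 / 0.5 | 8.9% | 49.3% v 45.9% | 3.4 | 4.0 |
| 0.25 / 0.33 | 14.5% | 47.7% v 42.3% | 5.4 | 6.5 |

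Over interaction ORs of 2 to 4 the loss runs from about 0.2 points to 6.4 at 100 v 100 and 7.0 at 100 v 200. An extreme severity OR of 0.1 gives about 27% shrinkage and a loss of 5 to 14 points.

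**4. Baseline EASI kept, and Firth's correction**

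With baseline EASI in both models and correlated with severity (100 v 100, interaction OR 3), the losses in the last three settings are 0.9, 2.5 and 4.1 points. A 4,000-replicate simulation with Firth's correction agrees with step 3: 48.2% v 47.6%, 49.1% v 45.8% and 45.6% v 40.5%.

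**5. Size of the test**

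With no true interaction, rejection in the simulation is 9.2% to 9.7% at nominal 10%.

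**The case against.** The best defence is that SAP 6.2.2.2 already restores both factors by default. That reading is possible, but its exception for models specified otherwise fits 6.14, which sets out a full list. So it shows an ambiguity and does not remove it.

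It is also fair that the protocol requires region only as appropriate, that baseline EASI or itch stays in two of the three models, and that Protocol 10.3.1 allows lesser analysis changes if they are justified in the study report. These points limit the size of the problem.

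A reader might infer more than the documents support:

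- **That the interaction test is invalid.** It is not; its size holds.
- **That power is certainly lost.** The loss depends on prognostic strengths the documents do not give. A separate Firth simulation with milder odds ratios (1.5 and 1.25) showed no loss: 39% without the strata, 37% with. Shrinkage is not guaranteed either. With 20% versus 50% at IGA 4 in the two subgroup levels and severity OR 0.33, a true interaction OR of 1.00 becomes 0.97.
- **That published subgroup odds ratios will disagree with the main model.** SAP 6.14 plans none; only p-values come from this model.
- **That every other SAP model adjusts for the strata.** The safety ANCOVA in 6.2.2.3 uses treatment and baseline value only.
- **That weight, BMI or race is strongly tied to region.** This is plausible with Japan as its own stratum, but the documents do not quantify it.

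**Conclusion.** The mismatch is real and worth correcting; its consequence is modest. SAP 6.14 as written omits two stratification factors that the protocol's subgroup model includes, and the SAP's default rule does not settle which applies. Under the assumptions in the working, omission costs between nothing and about 7 points of interaction power, and about 1 to 4 points where baseline EASI is kept, for all but the mildest setting. IGA (0,1) has no such protection.

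These tests are weak under either model: the adjusted version has only about 27% to 68% power at 100 v 100 for interaction odds ratios of 2 to 4. The subgroup analyses carry no multiplicity control, and primary and key secondary inference does not depend on them.

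**What to change.** In SAP 6.14, keep the listed terms and add baseline disease severity (IGA) and region (as appropriate). Leave severity out when it is the subgroup. Leave region out for all three geographic subgroups: region, Europe versus other, and Japan versus other. The last two are exact functions of the three-level region factor, so keeping it would make the subgroup main effect inestimable. If the sponsor prefers the shorter model, state and justify the departure from Protocol 10.3.6.2 in the SAP and the study report.

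SAP 6.16 says the 24-week interim has been conducted, so Week 16 subgroup results may already exist. Present the corrected fit as the protocol-specified model for EASI75, and as its counterpart for the other two endpoints, alongside anything already produced rather than in place of it.

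The cost is a sentence and two factors per model. The small downside is extra terms in sparse models, which the planned Firth correction helps to handle.
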